Protocol

The prediction of failure rate of dental implants

NCT number: Unknown yet

Document date: 21-9-2018

During the past decades, dental implant therapy has developed into a successful treatment option for patients confronted with both partial and complete edentulism. Based on the literature, the survival rate of dental implants, which is defined that the dental implants are still in the mouth after insertion, is around 95% in the 5-year follow-up and around 90% in the 10-year follow-up [1-3]. The success rate of dental implants, which is defined as dental implants in function, with good hard and soft tissue physiology and user satisfaction ranges from 85.2% to 88.7% in the follow-up of up to 20 years [4-6]. This indicates that both the success rate and survival rate of dental implants is high. However, both survival rates and success rates vary across patients with different profiles. The expense of dental implant treatment is high and implant placement is a surgical procedure which is invasive and thus risky for the patients' health. Once the failure of dental implants occurs, it may cause some severe negative consequences for patients. For example, the failure will cause a financial loss for patients and a possible shock concerning both mental and physical aspects. To reduce these risks it is important and necessary for clinicians to be able to predict the risk of the failure of dental implants of individual patients before they undergo dental implant treatment.

Aim:

The aim of the project is to identify important risk factors for failure of dental implants and to develop a prediction model for the failure rate of dental implants at follow-up as a tool for clinicians to establish patients individual risk profile.

Methods:

Study design

The study is a retrospective design. The clinical data of all the adult patients who were referred to the Department of Oral Implantology and Prosthetic Dentistry, Academic Centre for Dentistry Amsterdam (ACTA) at their first intake for placement of dental implant(s) from September 2009 to September 2013 are collected retrospectively from the clinical data management system of ACTA in the study.

Predictors

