The univariate and multivariate Cox regression analysis is used to identify important risk factors for the failure of dental implants and to develop the model. Then, the performance of the models, in aspects of calibration and discrimination, is assessed. Calibration is defined as the agreement between predicted outcomes and observed outcomes. For assessment of calibration, the included implants are separately grouped into deciles based on their predicted risk of failure. The calibration of the model is assessed by plotting the predicted risk of failure against 1 minus the individual Kaplan-Meier estimate for each decile in the follow-up. Discrimination is defined as the ability of the model to differentiate between those with and without outcome events. The discrimination of the model in the follow-up is assessed with the concordance index (C-index). Then, the model is converted to a score chart and line chart in order to facilitate the calculation of the failure rate of implants. The score of each included predictor is produced by the regression coefficients being divided by the smallest regression coefficient among the predictors and subsequently rounded. Finally, the clinical values of the model are assessed, using prevalence, sensitivity, specificity, positive predictive value (PPV), and negative predictive value (NPV) of the model at the optimal cutoff score.

All the statistical procedures are performed with SPSS software 25.0 (IBM, New York, the USA) and R software 3.2.3 (R Development Core Team, Vienna, Austria).

What is already known:

Recently, there are many studies focusing on the evaluation of survival rate of implants based on longitudinal cohorts. However, they mainly reported the values of the failure rate of implants in the follow-up (like 5-year survival rate) or compared the failure rate of different types of implants. These types of studies are beneficial for the groups of patients but not for the individual patients. Also, there are several studies focusing on the prognostic factors that may be associated with the survival rate of dental implants. But these studies belonged to prediction factor studies instead of prediction modeling studies. The findings in these studies are difficult to directly apply to clinical practice.

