However, there is a very limited number of studies focusing on the prediction of survival rate (or failure rate) of implants in the follow-ups. For example, Chuang et al. (1) used a clustered marginal approach to predict the survival rate in 2002 and found that among those who had a delayed procedure, did not smoke, and underwent a two-stage implant procedure, the predicted 1- and 5-year survival rates were 97.2% and 93.4%, respectively. For those who had an immediate implant placed, smoked, and underwent a one-stage procedure, the predicted survival rates were 58.5% and 27.6%, respectively. In 2006, Chuang and Cai (2) used Cox proportional hazards frailty model to predict the future implant survival based on some predictors including smoking status, the timing of placement of the implant and implant staging.

In this study, they predicted that for a non-smoking individual with 2 implants placed, an immediate implant and in one stage, the probability that 1 implant would survival 12 months was 85.8% and the joint probability of surviving for 12 months was 75.1%. If 1 implant was placed earlier and had survived for 12 months, then the second implant had an 87.5% chance of surviving 12 months. However, in these two studies, the authors only included a small number of predictors and did not develop a score chart for the individual patients. Also, the performance of the models was not assessed.

What is the project will add:

The project can provide clinicians with the predicted probability of the failure rate of dental implants of each individual patient preoperatively. The model may be helpful for clinicians to make decisions about the postoperative care for the patients. Also, the model can help shape the patients' expectations about the survival of dental implants.

What is new:

In the project, we will use some more predictors to predict the survival rate of dental implants to make the prediction model more accurate. Also, we will develop a score chart for clinicians. In this score chart, clinicians can easily calculate the sum score of each patient and find out the corresponding predicted probability of the failure rate of dental implants of each individual patient. The score chart is very easy-to-use in the clinical practice. Besides, in this project, the methodology (the prediction model developed with Cox regression analysis) is novel in dentistry.

References:

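### Clinical value is judged at one undefined optimal cutoff, with no decision threshold or error trade-off, so the plan will not show whether the rule beats flagging all or no implants where clinicians would act

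*Combined protocol and SAP*

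**What the plan says.** In the combined protocol and SAP, the Statistical analysis section first plans a decile calibration plot and a C-index ("Then, the performance of the models, in aspects of calibration and discrimination, is assessed"). It then converts the model to a rounded score chart. The last step is the test of clinical value: "Finally, the clinical values of the model are assessed, using prevalence, sensitivity, specificity, positive predictive value (PPV), and negative predictive value (NPV"), reported "of the model at the optimal cutoff score".

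There is one cutoff. No criterion for optimal is given, and no risk threshold, cost ratio or time point is attached to these measures. Net benefit, a decision curve, or an explicit comparison with treating all or no implants as high risk appears nowhere in the document.

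The section on what the project will add names two uses. One is decision support: "The model may be helpful for clinicians to make decisions about the postoperative care for the patients". The other is information: "the model can help shape the patients' expectations about the survival of dental implants". The introduction adds the wish "to predict the risk of the failure of dental implants of individual patients before they undergo dental implant treatment". None of these passages names a specific decision or the risk at which it would change.

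**The concern.** Sensitivity, specificity, PPV and NPV at one cutoff describe how a rule sorts implants. Whether the rule is worth using also depends on how bad a missed failure is relative to a false alarm, and on what would be done without the model. The plan states neither.

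The cutoff carries a trade-off all the same. Under the common criterion of maximum sensitivity plus specificity, that trade-off follows from the failure rate in the cohort and not from a clinical judgement. The same set of accuracy figures may then belong to a useful rule or to one that does worse than handling all implants alike, depending on a threshold that is never named. The calibration plot and C-index do not settle this, because neither involves a decision or a default strategy. The question remains even with complete follow-up and full validation.

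**Working it through.** The plan gives no cutoff, accuracy value, C-index or threshold, so there is no figure of its own to reproduce. What follows is illustration.

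**Inputs from the document (introduction).** Survival of about 95% at 5 years and 90% at 10 years implies loss of about 5% and 10%. Success "ranges from 85.2% to 88.7% in the follow-up of up to 20 years", so non-success is 100 − 88.7 = 11.3% to 100 − 85.2 = 14.8%. The plan's failure definition is broader than loss, so these serve only as plausible failure rates.

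**Assumptions, not in the document.** The optimal cutoff maximises sensitivity plus specificity; the model is well calibrated; the score is treated as continuous; C-index 0.65 to 0.80; censoring is ignored. The thresholds below are for arithmetic only and are not proposals.

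**Step 1: where the cutoff falls.** Let p be an implant's predicted risk and π the average risk. Sensitivity plus specificity is largest when an implant is flagged if p/π > (1 − p)/(1 − π), that is, if p > π. This choice is best only for someone who counts one missed failure as (1 − π)/π false alarms:

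- π = 5%: 0.95/0.05 = 19
- π = 10%: 0.90/0.10 = 9
- π = 15%: 0.85/0.15 = 5.7

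**Step 2: accuracy at that cutoff.** With logistic-normal risks, mean 10% and C-index 0.70, sensitivity is 0.646 and specificity 0.643. As fractions of all implants:

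- true positives 0.10 × 0.646 = 0.0646
- false positives 0.90 × 0.357 = 0.3213
- flagged 0.386
- PPV 0.0646/0.386 = 0.167
- NPV (0.90 × 0.643)/(0.90 × 0.643 + 0.0354) = 0.942

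**Step 3: net benefit at action threshold t.** For the rule, NB = TP − FP × t/(1 − t). For flagging everyone, NB = π − (1 − π) × t/(1 − t). For flagging no one, NB = 0.

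| t | Rule at the single cutoff | Flag all | Flag none | Same model cut at t |
|---|---|---|---|---|
| 5% | 0.0646 − 0.3213/19 = 0.048 | 0.10 − 0.90/19 = 0.053 | 0 | 0.057 |
| 10% | 0.0646 − 0.3213/9 = 0.029 | 0.10 − 0.90/9 = 0 | 0 | 0.029 |
| 20% | 0.0646 − 0.3213/4 = −0.016 | 0.10 − 0.90/4 = −0.125 | 0 | 0.007 |

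One set of accuracy figures is thus worse than flagging everyone at 5%, better than both defaults at 10%, and worse than flagging no one at 20%.

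**Step 4: the window in which the rule wins.** The rule beats flagging no one when t < PPV, and beats flagging everyone when t > 1 − NPV. Here that is 1 − 0.942 = 5.8% to 16.7%. At the same 10% failure rate with C-index 0.80 it is about 4.0% to 22.4%, which contains both 5% and 20%.

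A second model (equal-variance binormal scores) gives the same pattern:

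| Failure rate | C-index | Window |
|---|---|---|
| 5% | 0.70 | 2.8% to 8.7% |
| 11.3% | 0.65 | 7.6% to 16.5% |
| 11.3% | 0.70 | 6.6% to 18.8% |
| 11.3% | 0.80 | 4.6% to 25.1% |
| 14.8% | 0.70 | 8.7% to 24.0% |

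**The case against.** The other side has several fair points.

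- **The criterion is unknown.** The plan says only that the cutoff is optimal. A reader might infer that it was picked on purely statistical grounds and that nobody weighed the errors. The text does not say so. What is documented is that the criterion and the trade-off are unstated, and every number above is conditional on the assumed criterion. With a rounded integer score, the cutoff would also fall only near the average risk, not exactly on it.
- **The planned figures are not empty.** Prevalence is the PPV of flagging everyone, and 1 minus prevalence is the NPV of flagging no one, so partial reference values will be in the report. A reader who supplied a threshold could work out net benefit at that cutoff, or read the window from 1 − NPV and PPV. The claim that these measures can say nothing about clinical value is therefore too strong.
- **The window may be wide enough.** In the 10%, 0.70 case, 5% and 20% lie just outside each end; between 5.8% and 16.7% the rule does better than either default. At 14.8% failures, 20% lies inside the window. No document supports any particular threshold.
- **The main product is a probability chart.** The aim is an individual risk profile. Shaping expectations needs calibrated probabilities and no cutoff, and nowhere is a patient to be managed by the cutoff.

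These points limit the concern but do not remove it. The plan itself poses the question of clinical value and claims a use in postoperative decisions, yet it supplies no threshold at which its figures could answer that question. The C-index is not known in advance, so the plan should not count on a favourable one.

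**Conclusion.** The concern holds as a gap in the plan's assessment of clinical value. With no criterion for the cutoff, no threshold and no trade-off, the planned figures will not show whether the rule improves on flagging all or none at the risk where clinicians would act. Under the assumed criterion and good calibration, it does so only within a window whose limits move with the failure rate and the C-index; across the cases shown, the lower limit runs from 2.8% to 8.7% and the upper from 8.7% to 25.1%.

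A reader might go further and infer that the model is worse than no model. The documents do not support that. In the illustration, the same model cut at the relevant threshold beats both defaults at 5%, 10% and 20%; what can do worse is the single dichotomy. The predicted probabilities, the calibration plot and the C-index are unaffected. This is a worthwhile and cheap improvement for the decision-support use, not an error that invalidates the model.

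**What to change.** In the Statistical analysis section, replace the single-cutoff assessment of clinical value with net benefit of the score chart against flagging all and flagging none, shown as a decision curve. The clinical team should name the decision the chart is meant to support and fix the range of risk thresholds before the outcome data are analysed. State the time point at which risk is evaluated, and estimate true and false positives with a method that allows for censoring, for example Kaplan-Meier failure estimates among flagged implants. Evaluate the rounded chart itself, since that is what clinicians would use. Keep sensitivity, specificity, PPV and NPV, with prevalence as context, as description at the prespecified thresholds. If an optimal cutoff is still reported, define its criterion.

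The cost is a few lines in R, which the plan already uses, one paragraph of text, and agreement on a threshold range. No new data are needed, and the predictors, coefficients and chart do not change. The result may show the model in a less favourable light than a single cutoff would.

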The initial list of potential predictors for the failure of implants is first determined based on previous literature and the Dutch Clinical Practice Guideline (KPR). Then, the list of the predictors is sent to the international experts from the International Team for Implantology (ITI) for further screening. Finally, the short list of the potential predictors is determined based on the experts' opinions and the availability of the predictors in the clinical data management system of ACTA. The potential predictors include five domains: patients' demographic characteristics, lifestyle habits, general health, dental health, and implant characteristics.

Outcomes

The outcomes include the follow-up time of implants and whether the failure of the implants is observed at the follow-up. The follow-up time is defined as a period in days starting from the date at the placement of suprastructure (baseline) to the date at the last follow up time or the

date when the failure is observed. The failure of implants is defined as the presence of peri-implantitis, presence of mobility of implants, or removal of the implants for any reasons, for instance, unacceptable performance in aspects of function, tissue physiology, esthetics, and patients' satisfaction after placement of suprastructure.

Statistical analysis

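### The 2x2 measures at the score cutoff have no stated time and no rule for censored implants, so prevalence, PPV and NPV could reflect length of follow-up

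*Combined protocol and SAP*

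**What the plan says.** Under Statistical analysis, the model is fitted by Cox regression, checked with Kaplan-Meier by decile and the C-index, and turned into a score chart. Then "the clinical values of the model are assessed, using prevalence, sensitivity, specificity, positive predictive value (PPV), and negative predictive value (NPV") at a cutoff. That sentence gives neither a year nor a treatment of censored implants.

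Under Outcomes there are two quantities. One is a follow-up time "starting from the date at the placement of suprastructure (baseline) to the date at the last follow up time" or to failure. The other is "whether the failure of the implants is observed at the follow-up". No minimum follow-up is set. Under Study design, patients enter "at their first intake for placement of dental implant(s) from September 2009 to September 2013", so the time available differs by up to four years even with full attendance.

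The year-specific figures elsewhere describe earlier literature. The opening background says that implant survival "is around 95% in the 5-year follow-up and around 90% in the 10-year follow-up". What is already known reports an earlier model in which "the predicted 1- and 5-year survival rates were 97.2% and 93.4%, respectively" for one profile, while for another "the predicted survival rates were 58.5% and 27.6%, respectively".

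**The concern.** The five measures need a failed/not-failed label for every implant. Failure accumulates over time, so the label means little without a year. The natural reading is that the observed status supplies it, although the plan does not say so. Under that reading, an implant last seen at six months without failure and one sound at eight years are both non-failures, while a failure in year seven counts the same as one in year one.

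A clinician reads PPV and NPV as how often implants above the cutoff fail and how often those below it do not. If these depend on how long this clinic's patients kept attending, they cannot be read as risk by any year or compared with another cohort. The chart probability and the plotted calibration values also need a year. In the earlier model cited by the protocol, failure risk for one profile is 1 - 0.972 = 2.8% at 1 year and 1 - 0.934 = 6.6% at 5 years. For the other it is 1 - 0.585 = 41.5% and 1 - 0.276 = 72.4%. The planned line chart may show a time, but the plan does not say.

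**Working it through.** The plan states no value for any of the five measures, no event count and no follow-up distribution. There is no planned figure to reproduce, and what follows is illustration only.

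**Inputs from the protocol.** Survival is about 95% at 5 years and 90% at 10. A constant hazard from the first gives 0.95² = 90.25% at 10 years, so the two agree. Intake closed in September 2013 and opened in September 2009. The protocol carries "Document date: 21-9-2018", which is 5 and 9 years later.

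**Assumptions.**
- The document date is taken as the end of data, since the plan gives no cut-off date.
- Follow-up starts at suprastructure placement, after intake, so 9 years from baseline cannot be reached by that date. Allowing about one year, near-full attendance gives 4-8 years. Patchy attendance is represented by 0.5-8 years. Both are uniform.
- 4/17 = 23.5% of implants lie above the cutoff, hazards are constant, and the hazard ratio is ln(0.75)/ln(0.92) = 3.45.
- Overall 5-year risk is 5% (protocol survival figure; group risks 10.7% and 3.2%) or 12% (not in the documents; group risks 25% and 8%).

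**Formulas.** With F5 the 5-year risk in a score group, λ = -ln(1 - F5)/5. For follow-up uniform on (a, b), the crude risk is 1 - [exp(-λa) - exp(-λb)]/[λ(b - a)]. PPV is the risk above the cutoff, NPV is 1 minus the risk below it, and prevalence is the weighted sum.

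Example, 12% case, above the cutoff: λ = -ln(0.75)/5 = 0.05754.
- 0.5-8 years: 1 - (0.97164 - 0.63110)/0.43152 = 21.1%.
- 4-8 years: 1 - (0.79442 - 0.63110)/0.23015 = 29.0%.

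| Case | Measure | By year 5 | Crude, 0.5-8 y | Crude, 4-8 y |
|---|---|---|---|---|
| 5% | Prevalence | 5.0% | 4.2% | 5.9% |
| 5% | PPV | 10.7% | 9.1% | 12.7% |
| 5% | NPV | 96.8% | 97.3% | 96.1% |
| 12% | PPV | 25.0% | 21.1% | 29.0% |
| 12% | NPV | 92.0% | 93.2% | 90.5% |

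A single common hazard at 5% risk gives crude prevalence of 4.2% and 6.0%.

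**Source of the shift.** The share of 5-year failures missed is 1 - mean[1 - exp(-λ·min(c, 5))]/F5, where c is follow-up, combined over the two groups. In the 5% case it is 27% with 0.5-8 years and 2% with 4-8 years. Of the failures counted, 13% and 18% occur after year 5.

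**The errors can cancel.** With 2-8 years, crude PPV in the 12% case is 1 - (0.89130 - 0.63110)/0.34522 = 24.6%, against 25%.

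**Front-loaded failure.** Both profiles of the earlier model put ln(0.972)/ln(0.934) = ln(0.585)/ln(0.276) = 0.416 of the 5-year cumulative hazard in year 1. Applied to the 12% case, crude PPV is 22.2% with 0.5-8 years. With 4-8 years it is 1 - (0.78216 - 0.66124)/0.16795 = 28.0%.

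**Sensitivity and specificity.** In both risk cases and both spreads they stay within 1 point of their 5-year values (12% case: sensitivity 48.9% and 48.5% against 49.0%; specificity 79.3% and 80.6% against 79.9%). If follow-up differs by score, sensitivity moves clearly. In the 12% case it is 56.9% when implants above the cutoff are followed 4-8 years and the rest 0.5-8, and 40.6% when this is reversed.

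**A year alone is not enough.** In the 5% case with 0.5-8 years, a share 3/7.5 = 0.4 of implants have potential follow-up of at least 5 years. Above the cutoff, 7.9% are seen to fail by year 5. Counting censored implants as non-failures gives PPV 7.9%. Dropping them gives 0.0790/(0.0790 + 0.4 × 0.8927) = 18.1%. The target is 10.7%.

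**The case against.** The plan records time as well as status, so status at any year can be derived from the planned data, and every other step is survival-based. A reader might infer that the plan commits to a crude ever-failed table. It does not: it leaves the choice open, and the bias is conditional on that choice.

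The size can also be overstated. The 12% risk has no support in the documents. The background also quotes success rates of 85.2% to 88.7% over up to 20 years, which are nearer to the plan's composite failure than survival is. Under a constant hazard they imply 5-year failure of 3.0-3.9% if read at 20 years (1 - 0.887^0.25 and 1 - 0.852^0.25), or 5.8-7.7% if read at 10 (1 - 0.887^0.5 and 1 - 0.852^0.5). The definitions differ and the time is vague, so this is no firm bound. It does make the 5% case the better anchor, and there the PPV error is -1.6 to +2.0 points.

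Individual risk reaches the clinician through the score chart, and PPV and NPV are a closing summary at one cutoff. Kaplan-Meier and IPCW also assume independent censoring within score group, which attendance-based records may violate. The documents do not say, and a table of follow-up by group cannot test it.

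All of this stands and limits the weight of the point. None of it supplies the missing year or censoring rule.

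**Conclusion.** The omission is certain from the text: no horizon and no censoring rule for the five measures. The consequence is conditional. If the observed status is used, prevalence, PPV and NPV depend on how long implants were followed. In the document-anchored 5% illustration, the same model and cutoff give a PPV of 9.1% or 12.7% according to attendance, a gap of 3.6 points around a 5-year value of 10.7%. In the assumed 12% case the gap is 7.9 points around 25%. These sizes rest on constant hazards, uniform follow-up, an assumed hazard ratio and an assumed share above the cutoff.

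Two stronger inferences are not supported. One is that the model itself is compromised: the Cox fit, score points, decile membership and C-index do not use this table. The other is that sensitivity and specificity are materially wrong: that needs follow-up related to the score, which the documents do not show. Nor is the direction of the PPV error known, since it depends on the follow-up actually achieved. The change should be made, but it concerns the performance summary and not the model.

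**What to change.** Name one main horizon, or a rule for choosing it from the numbers still at risk, set before performance is examined. Use it for the chart probability, the plotted calibration values and the 2x2 step. Report prevalence as 1 minus Kaplan-Meier at that horizon. Estimate sensitivity, specificity, PPV and NPV with Kaplan-Meier within score group or with IPCW; either is acceptable. Report follow-up by score group. In the same edit, state the criterion that makes the cutoff optimal.

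The cost is a few sentences and standard survival code in the R software already named. No new data are needed and the fitted model does not change. Intervals widen when many implants are censored before the horizon. In a simulation of 1000 implants (12% case, 0.5-8 years, 5-year horizon), the standard error of PPV was 3.5 points against 2.7 for the crude proportion with independent implants, and 4.2 against 3.5 with four correlated implants per patient. The mean Kaplan-Meier PPV was 25.0%, the true value. The independent-censoring assumption, within score group, is the one the Cox and Kaplan-Meier steps already make.

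### The failure probability offered before surgery covers only implants that reach suprastructure, and two sentences call it survival although the event includes disease and mobility

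*Combined protocol and SAP*

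**What the plan says.** **Moment of use.** The opening section gives the reason for the project as knowing an individual's failure risk before treatment begins. *What is the project will add* repeats this by offering "the predicted probability of the failure rate of dental implants of each individual patient preoperatively".

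**What is modelled.** In *Outcomes*, the clock is set as follows: "The follow-up time is defined as a period in days starting from the date at the placement of suprastructure (baseline"). The event is also set there: "The failure of implants is defined as the presence of peri-implantitis, presence of mobility of implants, or removal of the implants for any reasons". The same sentence ends by placing failure after suprastructure placement.

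**What the output is called.** The title, *Aim*, *Outcomes* and *Statistical analysis* all say failure. So does the score chart sentence in *What is new*, where clinicians will "find out the corresponding predicted probability of the failure rate of dental implants of each individual patient". Two other sentences about the project's own output say survival. *What is new* announces that "we will use some more predictors to predict the survival rate of dental implants", and *What is the project will add* says the model can help shape patients' "expectations about the survival of dental implants".

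**What survival means here.** The only definition is in the opening section: "which is defined that the dental implants are still in the mouth after insertion". Success is defined separately: "which is defined as dental implants in function, with good hard and soft tissue physiology and user satisfaction". No later section redefines either term.

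**The concern.** The moment at which the prediction is to be given and the moment at which the model starts counting are different. Before surgery, nobody knows which implants will reach suprastructure. The model describes only those that do, and no section states this condition. A patient given the score before surgery would naturally take it to cover everything that can go wrong from then on, including early loss.

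The survival wording adds a second, smaller problem. A patient told about survival hears the chance of keeping the implant. The model gives the chance of avoiding a composite that includes disease and mobility in implants that are still in place. The tool is meant for individual risk communication, so what the number stands for matters to the person hearing it.

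**Working it through.** The plan states no figure on this point, so there is none to reproduce. The check compares definitions.

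**1. The same implant under the two definitions.**

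| Course of the implant | Survival (opening section) | Model (*Outcomes*) |
|---|---|---|
| Lost between insertion and suprastructure | Lost | Not in the model: no baseline date |
| Peri-implantitis or mobility, still in the mouth | Surviving | Event |
| Removed after suprastructure | Lost | Event |
| None of these | Surviving | No event |

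The first two rows disagree. The first row is the time-origin point and also affects the claim worded as failure. The second row affects only the survival wording.

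**2. Direction.** Let *e* be the proportion of implants lost before suprastructure. Among implants that reach it, let *p* be the composite risk and *r* the removal risk, both at the same time after suprastructure. Removal is a component of the composite, so *r* ≤ *p*.

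- Failure seen from before surgery, with early loss counted as failure: *e* + (1 − *e*)*p*. This differs from the score by *e*(1 − *p*), which is never negative.
- Loss seen from before surgery: *e* + (1 − *e*)*r*. This differs from the score by *e*(1 − *r*) − (*p* − *r*). The first term is zero or positive and the second subtracts zero or more, so the net sign depends on values that the documents do not give.

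**3. Illustration with assumed inputs.** None of these values comes from the documents. Take *p* = 10%.

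- Failure from before surgery, *e* = 1%: 0.01 + 0.99 × 0.10 = 10.9%.
- Failure from before surgery, *e* = 5%: 0.05 + 0.95 × 0.10 = 14.5%.
- Loss from before surgery, *e* = 1% and *r* = 2%: 0.01 + 0.99 × 0.02 = 3.0%, below the 10% score.
- Loss from before surgery, *e* = 5% and *r* = 9%: 0.05 + 0.95 × 0.09 = 13.6%, above the 10% score.

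These show only that either sign is possible. They do not estimate the gap in this cohort.

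**4. Can the cited rates size it?** The opening section cites survival of about 95% at 5 years and about 90% at 10 years, and success of 85.2% to 88.7% in follow-up of up to 20 years. The protocol thus treats the two as different quantities. Their difference cannot serve as the gap, because the horizons differ and neither is the composite in *Outcomes*.

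**5. How far the survival wording goes.** The two closing sections describe the project's own output four times, twice as failure and twice as survival. Only one of the survival sentences says the project will predict survival; the other, about expectations, implies it. The preoperative claim is in a separate sentence that says failure.

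**The case against.** The strongest reply is that the survival point is one of wording. The operative text says failure throughout. *What is already known* gives a 5-year survival rate as an example of a failure rate, and its last part puts the two terms side by side as alternatives. *Statistical analysis* compares predicted failure with one minus a Kaplan-Meier estimate. On that reading, survival is loose shorthand for the complement of failure, and the definition in the opening section only introduces published rates. This largely stands: taken alone, the survival wording is close to a clerical matter. It does not remove the ambiguity for a reader who goes by the only definition given.

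The reply does not reach the preoperative claim. That sentence already says failure, and the mismatch lies in the time origin.

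Three stronger readings are tempting, and the documents do not support them:

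- *The model cannot be used before surgery.* Nothing shows this. A risk from suprastructure onward can be quoted in advance if it is stated as conditional on reaching that point. The plan names predictor domains, not individual predictors, so it cannot be inferred that they are unknown before surgery.
- *The score chart will be labelled survival.* The chart sentence says failure.
- *The outcome or the Cox analysis is wrong.* The event, the clock and the analysis agree with one another. Only the stated use goes further than they do.

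**Conclusion.** The point holds as a limit on what the project may claim. The preoperative promise is wider than the design supports, because losses before suprastructure can never be events. The two survival phrases are a lesser inconsistency in the same closing sections.

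If early loss is counted as failure, the time-origin gap alone makes the score too low whenever any implant is lost before suprastructure. Once the score is read as the chance of losing the implant, disease and mobility pull the other way and the net direction is undetermined. The documents cannot give a size for either case.

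The conclusion rests on two readings: that survival keeps the meaning given in the opening section, and that an implant without a suprastructure date has no follow-up time. No planned estimate or performance measure changes. This is a cheap improvement.

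**What to change.** Keep the composite outcome, the time origin and the Cox model.

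- In the two closing sections and on the score and line charts, name the output *probability of peri-implantitis, mobility or removal after suprastructure placement, among implants that reach suprastructure*.
- Qualify the claim of prediction before treatment in the same way, both in the opening section and in *What is the project will add*.
- Replace the two survival phrases with that wording.
- Report first events by component. Put components found on the same date in their own row where the record shows them.
- From the same records, where available, report how many implants placed in the cohort never reached suprastructure. Without this count the size of the preoperative gap stays unknown.

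The cost is a narrower claim and one or two descriptive tables. Coding failure already requires finding the first qualifying component. The same-date row asks for slightly more, since every component must then be checked. The component table shows first events, not every later removal, because follow-up ends at the first failure; its caption should say so.
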